### **6.3.5 Anticipated risks and safety concerns of the study drug**

Appropriate eligibility criteria and specific DLT definitions, as well as specific dose modification and stopping rules are included in this protocol. Prophylactic or supportive treatment for expected toxicities, including management of study-drug induced adverse events will be as per institutional guidelines.

Refer to preclinical toxicity [REDACTED] and clinical data found in the [nazartinib and capmatinib Investigator’s Brochure].

## **6.4 Concomitant medications**

### **6.4.1 Permitted concomitant therapy**

In general, concomitant medications and therapies deemed necessary for the supportive care (e.g. such as anti-emetics, anti-diarrhea) and safety of the participant are allowed, except when specifically prohibited (see Section 6.4.3).

The participant must be told to notify the investigational site about any new medications he/she takes after the start of the study drug. All medications (other than study drug) and significant non-drug therapies (including physical therapy, herbal/natural medications and blood transfusions) administered during the study must be listed on the Concomitant Medications or the Surgical and Medical Procedures CRF.

Each concomitant drug must be individually assessed against all exclusion criteria/prohibited medication. If in doubt, the investigator should contact the Novartis medical monitor before enrolling a participant or allowing a new medication to be started. If the participant is already enrolled, contact Novartis to determine if the participant should continue participation in the study.

#### **6.4.1.1 Permitted concomitant therapy of capmatinib in combination with nazartinib**

Anticoagulation treatment is also allowed if INR has been established within the therapeutic range prior to study entry. PT and PTT  $\geq 1.5$ x ULN are permitted in these cases.

After discussion with Novartis, participants who develop progressive disease limited to the bone or CNS may undergo radiotherapy to the bone or CNS, and surgical resection of CNS metastases, and remain on study. Nazartinib and capmatinib should be held for at least 5 days prior to radiotherapy or surgery. Nazartinib and capmatinib may be resumed  $> 3$  days after completing radiotherapy or surgery if all procedure-related toxicities have resolved to  $\leq$  Grade 1.

The exception to this is palliative bone radiation, which is permitted throughout the study. However, study treatment should be interrupted on the day of radiotherapy.

No drug-drug interaction is expected between capmatinib, nazartinib and bisphosphonates as the drugs are eliminated through different elimination pathways. Bisphosphonates are not inhibitors of human CYP450 enzymes involved in the metabolism of capmatinib and nazartinib and do not undergo metabolism in vivo.

#### **6.4.1.2 Permitted concomitant therapy of capmatinib monotherapy in Phase II Group 5**

The following restrictions apply during the entire duration of the study:

- No other investigational therapy should be given to participants
- No anticancer agents other than the study medication should be given to participants

Participants are permitted to use the following medications while taking study drug:

- Antibiotics
- Medications to prevent or treat nausea, vomiting or diarrhea
- Growth factors (e.g., Granulocyte-Colony-Stimulating Factor (G-CSF), Granulocyte-Macrophage Colony-Stimulating Factor (GM-CSF), erythropoietin, platelets growth factors, etc.) are allowed per the investigator's judgement and per local guidelines
- Oxygen therapy and blood products or transfusions
- Nutritional support or appetite stimulant
- Pain medication

#### **6.4.2 Permitted concomitant therapy requiring caution and/or action**

##### **6.4.2.1 Permitted concomitant therapy of capmatinib in combination with nazartinib requiring caution and/or action**

[REDACTED]

#### **Interactions with transporters**

[REDACTED]

[REDACTED]

The participant and the Investigator should be aware of potential signs of overdose of the concomitant medication. In the event of suspected toxicity, administration of either nazartinib, Capmatinib or concomitant drugs should be discontinued according to Investigator judgment.

Refer to [Table 14-14](#) in [Section 14.3](#) Appendix for permitted medications that require caution when concomitantly used with nazartinib and capmatinib. If a medication listed in [Section 14.4](#) Appendix appears on both the list of prohibited and the list of medications to be used with caution ([Table 14-14](#) and [Table 14-16](#)), the medication is prohibited.

[REDACTED]

[REDACTED]

[REDACTED]

[REDACTED] Refer to [Table 14-15](#) in [Section 14.3 Appendix](#) for a list of the permitted concomitant medications requiring caution with capmatinib monotherapy. If a medication listed in [Section 14.4 Appendix](#) appears on both the list of prohibited and the list of medications to be used with caution ([Table 14-15](#) and [Table 14-17](#)), the medication is prohibited.

### **6.4.3 Prohibited concomitant therapy**

If during the course of the trial prohibited concomitant medication cannot be avoided study treatment must be interrupted until an assessment of the potential safety risk has been performed.

#### **6.4.3.1 Prohibited concomitant therapy with capmatinib and nazartinib**

##### **Antineoplastic therapies**

Concomitant antineoplastic therapy (including radiotherapy and surgery) or other investigational treatment is prohibited except as described in [Section 6.4.1](#).

[REDACTED]

[REDACTED]

[REDACTED]

[REDACTED]

[REDACTED]

[REDACTED]

##### **Live vaccines**

Live vaccines (e.g., intranasal influenza, measles, mumps, rubella, oral polio, BCG, yellow fever, varicella, and TY21a typhoid vaccines, COVID-19 vaccines) must not be administered while a participant is dosed with capmatinib + nazartinib and for 30 days after the last dose of study treatment (capmatinib + nazartinib).

##### **Drug with a known risk of QT prolongation**

Medications with a known risk to prolong the QT interval and/or known to cause Torsades de Pointe should not be administered while a participant is dosed with capmatinib + nazartinib and for 30 days after the last dose of study treatment (capmatinib + nazartinib). Such medications

should be discontinued within 5 half-lives or 7 days prior (whichever is longer) to starting study drug or replaced by safe alternative medication. A list of drugs with a known risk to prolong the QT interval and/or known to cause Torsades de Pointe is provided in [Table 14-16](#) in [Section 14.3](#) Appendix and available online at [qtodrugs.org](http://qtodrugs.org). Refer to [Table 14-16](#) in [Section 14.3](#) Appendix for a list of prohibited medications. If a participant must use a drug in [Table 14-16](#) in [Section 14.3](#) Appendix, the participant must be discontinued from the study.

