### **After confirming ECG reading at site, if QTcF > 500 ms**

- Interrupt study treatment (capmatinib + nazartinib)
- Repeat ECG and confirm ECG diagnosis by a cardiologist or central ECG lab
- If QTcF confirmed > 500 ms:
  - Correct electrolytes, eliminate culprit concomitant treatments, and identify clinical conditions that could potentially prolong the QT
  - Consult with a cardiologist (or qualified specialist)
  - Increase cardiac monitoring as clinically indicated, until the QTcF returns to  $\leq 480$  ms.
  - Repeat ECGs 7 days and 14 days (and then every 21 days) after dose resumption for all participants who had therapy interrupted due to QTcF > 500 ms.
- After resolution to  $\leq 480$  ms, consider re-introducing study treatment (capmatinib + nazartinib) at reduced dose, and increase ECG monitoring:
  - If QTcF remains  $\leq 500$  ms after dose reduction, continue planned ECG monitoring during subsequent study treatment
  - If QTcF recurs > 500 ms after dose reduction, discontinue participant from trial.

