### 7.1.4 Discontinuation from study treatment and from study

Participants may voluntarily discontinue from the study treatment for any reason at any time. If a participant decides to discontinue from the study treatment, the investigator should make a reasonable effort (e.g. telephone, e-mail, letter) to understand the primary reason for this decision and record this information in the participant's chart and on the appropriate CRF pages. They may be considered withdrawn/opposition to use data/biological samples, if they state an intention to withdraw/opposition to use data/biological samples, fail to return for visits, or become lost to follow-up for any other reason.

The investigator must discontinue study treatment for a given participant if he/she believes that continuation would be detrimental to the participant's well-being.

Discontinuation from study treatment is required under the following circumstances:

- Adverse events and laboratory abnormalities meeting criteria for study treatment discontinuation: refer to [Section 6.3](#).
- Pregnancy
- Interruption of one of the study drugs for 21 consecutive days or more, regardless of reason for study drug interruption
- Use of prohibited treatment, refer to [Appendix 4](#).
- Any other protocol deviation that results in a significant risk to the participant's safety.

Participants who discontinue from study treatment agree to return for the end of treatment and follow-up visits indicated in the Assessment Schedule (refer [Section 7](#)). In addition, before a new anti-neoplastic therapy is initiated for a participant, it is strongly recommended to perform a tumor assessment. If they fail to return for these assessments for unknown reasons, every effort (e.g. telephone, email, letter) should be made to contact them as specified in [Section 7.1.7](#).

For Phase II, the investigator must also contact the IRT to register the participant's discontinuation from study treatment.

Discontinuation from study is when the participant permanently stops receiving the study treatment, and further protocol-required assessments or follow-up, for any reason.

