## 14.4 Appendix 4 - Prohibited concomitant medications

**Table 14-16 Prohibited concomitant medications with capmatinib and nazartinib**

Mechanism of Interaction	Drug Name
Strong CYP3A4 inhibitor	boceprevir, clarithromycin, cobicistat, conivaptan, grapefruit juice  , indinavir, itraconazole, ketoconazole, mibefradil, nefazodone, nelfinavir, posaconazole, ritonavir, saquinavir, telaprevir, telithromycin, voriconazole, troleandomycin, danoprevir/ritonavir, eltegravir/ritonavir, indinavir/ritonavir, lopinavir/ritonavir (HIV), saquinavir/ritonavir, tipranoavir/ritonavir
Strong CYP3A4 inducer	avasimibe, carbamazepine, enzalutamide, mitotane, phenobarbital, phenytoin, rifabutin, rifampin, St. John's wort
CYP1A2 substrate with NTI	theophylline, tizanidine
CYP2C8 substrate with NTI	Paclitaxel
CYP2C9 substrate with NTI	phenytoin, warfarin
CYP2C19 substrate with NTI	(S)-mephenytoin
CYP3A4 substrate with NTI	alfentanil, astemizole, cisapride, cyclosporine, diergotamine, dihydroergotamine, ergotamine, fentanyl, pimozide, quinidine, sirolimus, tacrolimus, terfenadine, thioridazine
P-gp substrate with NTI	cyclosporine, digoxin, fentanyl, paclitaxel, phenytoin, quinidine, sirolimus, tacrolimus
Source: Adapted from Oncology Clinical Pharmacology Drug-Drug Interaction Database (release date: April 2015) which was compiled from the Indiana University School of Medicine's "Clinically Relevant" Table and supplemented with the FDA Draft Guidance for Industry, Drug Interaction Studies – Study Design, Data Analysis, and Implications for Dosing and Labeling (February 2012), and the University of Washington's Drug Interaction Database. The lists provided may not be exhaustive. NTI: narrow therapeutic index	
Live vaccines	e.g., intranasal influenza, measles, mumps, rubella, oral polio, BCG, yellow fever, varicella, and TY21a typhoid vaccines, COVID-19 vaccines

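### For a participant on the combination who must take a Table 14-16 drug, Sections 6.4.3, 7.1.4 and 6.4.3.1 are not reconciled, and removal from the study as 7.1.4 defines it contradicts the follow-up required by 6.3.4 and 7.1.6

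*Protocol*

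**What the plan says.** Three parts of the protocol address use of a prohibited drug.

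- Section 6.4.3, in general terms: if "prohibited concomitant medication cannot be avoided study treatment must be interrupted until an assessment of the potential safety risk has been performed".
- Section 7.1.4: under the sentence "Discontinuation from study treatment is required under the following circumstances", one listed item is "Use of prohibited treatment, refer to" Appendix 4.
- Section 6.4.3.1, in the paragraph on drugs with a known QT risk: if a Table 14-16 drug must be used, "the participant must be discontinued from the study".

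Table 14-16, headed "Prohibited concomitant medications with capmatinib and nazartinib", stands in Appendix 4 (Section 14.4), so 7.1.4 and 6.4.3.1 act on the same list.

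Section 7.1.4 distinguishes two exits. Those who stop study treatment return for end-of-treatment (EOT) and follow-up visits. The other exit is defined thus: "Discontinuation from study is when the participant permanently stops receiving the study treatment, and further protocol-required assessments or follow-up, for any reason".

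Section 6.3.4.1 uses similar language for a different trigger: "If QTcF recurs > 500 ms after dose reduction, discontinue participant from trial".

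**The concern.** The same event leads to a pause, a stop of treatment or an exit from the study, depending on which section the site reads. The third outcome differs in kind. Taken with the protocol's own definition, it ends observation as well as dosing.

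The trigger is a medical need that arises after baseline. The QT row of Table 14-16 includes ondansetron, levofloxacin, moxifloxacin and clarithromycin, and Table 6-16 itself mentions fluoroquinolones for complicated diarrhea. Participants who need such drugs may differ in toxicity or prognosis from those who do not. If they left follow-up, safety observation would stop just when an interaction or a QT effect is the worry. Their PFS, DOR and OS times would also be censored for a reason that may be related to outcome.

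**Working it through.** No stated figure is in dispute and no sample-size or power formula applies. The check sets the sections side by side.

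**1. Action on study drug**

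| Section | Trigger | Action |
|---|---|---|
| 6.4.3 | Prohibited drug unavoidable | Interrupt until risk assessed |
| 7.1.4 | Use of an Appendix 4 treatment | Discontinue study treatment |
| 6.4.3.1 | Must use a Table 14-16 drug (combination) | Discontinue from the study |

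The first could be a holding step before either of the others, but no section says so or says what follows the assessment. The second and third are separate outcomes under 7.1.4.

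**2. Follow-up after each outcome**

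| Follow-up | Treatment stopped only | Discontinued from study (7.1.4 definition) |
|---|---|---|
| EOT visit | Required (7.1.4) | Ends |
| 30-day safety | All participants (6.3.4, 7.1.6) | Ends |
| Tumor assessments | Every 8 weeks until progression or another listed end point (7.1.6) | Ends |
| Survival | Every 3 months, not Group 5 (7.1.6) | Ends |

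The exceptions in 7.1.6 do not include prohibited-drug use. For tumor assessments they are death, progression, loss to follow-up, consent withdrawal or opposition, and study termination. For survival they are consent withdrawal and loss to follow-up. So 6.4.3.1, read with the definition, contradicts 7.1.6.

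**3. The QTcF rule.** Section 6.3.4 requires follow-up of an adverse event that stops treatment: at least weekly for 4 weeks, then about every 4 weeks until it resolves or stabilizes. Section 7.1.6 repeats the end point. Table 6-16 calls for repeat ECGs when QTcF of 501 ms or more recurs. Removal from the trial under 6.3.4.1, taken literally, cannot be squared with these.

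**4. Which endpoints are exposed (Section 10.7.2.1)**

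- PFS and DOR without an event are censored at the last adequate tumor assessment, so ending scans moves the participant into that category.
- OS is censored at last contact for participants alive at cut-off, withdrawn from consent or lost. Removal by rule is not named.
- Best overall response in Phase Ib and Groups 1 to 4 ignores scans more than 28 days after the last dose. Scheduled scans are 8 weeks apart (8 × 7 = 56 days). Even with both ±7-day windows used up, the gap is 56 − 14 = 42 days, which exceeds 28. At most one scheduled scan can fall inside the window, plus any EOT or off-schedule confirming scan.

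**5. Size.** Any bias depends on how many participants need a Table 14-16 drug and how their later hazard compares with the rest. The protocol states neither, so no figure can be derived.

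**The case against.** The strongest reply is that follow-up is mandated elsewhere in plain terms. Section 6.3.4 and Section 7.1.6 require 30-day safety follow-up of all participants, Section 8.2.2 requires every SAE to be reported until 30 days after treatment stops, and 7.1.6 continues tumor and survival follow-up without excepting this case. The protocol also uses the phrase loosely: Section 7.2.1 speaks of participants discontinuing from the study for progression, yet 7.1.6 keeps those participants in survival follow-up. A site could reasonably take 6.4.3.1 to mean stopping treatment. This stands as a limit on the consequence: data loss is possible, not established. It does not remove the defect, because 7.1.4 defines the phrase and the site must choose between two instructions.

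Interruption followed by discontinuation can also be read as a sequence. That is fair. The firmest conflict is between stopping treatment and leaving the study.

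On scope, the sentence sits under a QT heading, and neighboring paragraphs of 6.4.3.1 are redacted, so handling of the other drug classes in Table 14-16 cannot be checked. Section 6.4.1.1 also permits anticoagulation with an established INR. Even if the sentence is confined to the QT row, the contradiction remains. It covers the combination only: Phase Ib, Groups 1 to 4 and the Group 5 extension. The Group 5 monotherapy primary endpoint is not reached by it.

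Finally, PFS and OS are descriptive secondary endpoints here, and PFS is already censored at new anticancer therapy. Both points limit what is at stake.

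**Conclusion.** The contradiction is certain; its effect on the data is conditional. The three sections do not agree on the study-drug action, and the words chosen in 6.4.3.1 and 6.3.4.1, under the protocol's own definition, end follow-up that 6.3.4 and 7.1.6 require. If sites act on those words, 30-day safety, PFS, DOR and OS data are lost in participants selected by medical need, and the censoring could be informative.

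A reader might infer that follow-up is in fact cut off, or that response rates and median PFS are distorted by a definite amount. The documents do not support either inference. The same protocol mandates continued follow-up, so practice may be unaffected. If the need for these drugs were unrelated to prognosis, the censoring would not bias the survival estimates. The frequency of use and the later hazard are not given. The 28-day rule keeps any effect on ORR small, confined to an EOT or confirming scan within that window.

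**What to change.** - Reconcile 6.4.3, 6.4.3.1 and 7.1.4 into one stated action on study drug when a prohibited drug is needed, including what follows the risk assessment. This review does not say which action is right.
- In 6.4.3.1 and 6.3.4.1, replace removal from the study or trial with wording under which the EOT visit, 30-day safety, tumor assessments and, where applicable, survival follow-up continue under 7.1.6 whatever action on study drug is chosen. Keep the defined term in 7.1.4 for participants who really leave all follow-up.
- In passing, correct the pointer in 6.4.3.1, which places Table 14-16 in Section 14.3; it stands in Section 14.4.

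The cost is wording in a few sections. The visits already exist for everyone who stops treatment, and no analysis or sample size changes.

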#### **6.4.3.2 Prohibited concomitant therapy with capmatinib monotherapy in Phase II Group 5**

[REDACTED]

#### **Live vaccines**

Live vaccines (e.g., intranasal influenza, measles, mumps, rubella, oral polio, BCG, yellow fever, varicella, and TY21a typhoid vaccines, COVID-19 vaccines) must not be administered while a participant is dosed with capmatinib monotherapy and for 30 days after the last dose of study treatment.

#### **6.4.4 Use of bisphosphonates or RANKL inhibitor**

Treatment with bisphosphonates or receptor activator of nuclear factor kappa-B ligand (RANKL) inhibitor for pre-existing bone metastases is permitted, if clinically indicated and at the investigator's discretion following existing local guidelines. Treatment with bisphosphonates or RANKL inhibitor should preferably begin before the study treatment is initiated, but can also be initiated during therapy only if absence of radiological bone disease progression is well documented (in this case, the reason for its use must be clearly documented, i.e., “pre-existing, non-progressing, bone metastases”).

#### **6.4.5 Permitted radiotherapy**

Localized palliative radiotherapy for pre-existing, painful bone/liver metastases is permitted. It should not be delivered to a target lesion. If palliative radiotherapy is initiated after start of study treatment, the reason for its use must be clearly documented and progression as per RECIST 1.1 must be ruled out. The study treatment must be interrupted on the days of radiotherapy and can be resumed the day after its completion. Caution is advised for radiation to fields that include lung tissue. The radiotherapy must be listed on the appropriate eCRF pages. After documented progression by RECIST 1.1, radiotherapy is allowed following the same dose adjustment guidance in case capmatinib and osimertinib is continued beyond PD.

## 6.5 Participant numbering, treatment assignment

This is a non-randomized trial and Integrated Response Technology (IRT) will only be used for distribution of study medication in the Phase II part.

### 6.5.1 Participant numbering

Each participant is identified in the study by a participant Number (Participant No.), that is assigned when the participant is first enrolled for molecular pre-screening and is retained as the primary identifier for the participant throughout his/her entire participation in the trial. The participant No. consists of the Center Number (Center No.) (as assigned by Novartis to the investigative site) with a sequential participant number suffixed to it, so that each participant is numbered uniquely across the entire database. Upon signing the molecular pre-screening or screening informed consent form, the participant is assigned to the next sequential participant No. available to the investigator through the EDC interface.

For Phase II participants, the investigator or designated staff will contact the IRT at the molecular pre-screening visit and at the screening visit to provide the requested identifying information for participant registration into the IRT.

Once assigned, the participant No. must not be reused for any other participant and the participant No. for that individual must not be changed, even if the participant is re-screened. If the participant fails to be assigned to treatment or start treatment for any reason, the reason will be entered into the Screening Disposition page.

IRT must be notified within 2 days that the participant was not enrolled.

### 6.5.2 Treatment assignment

The assignment of a participant to a particular cohort will be coordinated by the sponsor during the Phase Ib part of the study.

For the Phase II part, an IRT will be used to track participant enrollment, document key eligibility criteria, allocate participants into 5 different groups based on their characteristics at study entry, and track individual assignment of capmatinib monotherapy or capmatinib in combination with nazartinib drug supplies. The IRT will dispense the selected capmatinib monotherapy or capmatinib in combination with and nazartinib dose to each participant participating in this trial.

For each allocated participant, and prior to dosing, all participants who fulfill all inclusion/exclusion criteria will be assigned to one of the groups of interest during the Phase II part, and information will be collected via IRT:

- Group 1 (first or second generation TKI resistant): EGFRmutL858R/ex19del NSCLC participants developing resistance to EGFR-TKI:
  - sub-group 1a: EGFRmutL858R/ex19del NSCLC with acquired mutation T790M (*T790M+*, *MET dysregulation-*).
  - sub-group 1b: EGFRmutL858R/ex19del NSCLC with demonstrated MET dysregulation (*T790M-*, *MET dysregulation+*).  
MET dysregulation is defined as either gene copy number  $\geq 4$  and/or IHC 3+ (defined as  $\geq 50\%$  of cells staining with high intensity)

- sub-group 1c: EGFRmutL858R/ex19del NSCLC with either evidence of both acquired T790M and MET dysregulation (*T790M+*, *MET dysregulation+*)
- sub-group 1d: EGFRmutL858R/ex19del NSCLC with MET dysregulation below the levels for sub-group b (*T790M-*, *MET dysregulation-*).
- Group 2 (EGFRmut, de novo T790M, any MET, 1/3L antineoplastic, EGFR TKI naïve): EGFR-TKI naïve NSCLC participants with T790M de novo mutation.
- Group 3 (EGFRmut, T790M negative, any MET, 1L antineoplastic): EGFRmutL858R/ex19del NSCLC participants, treatment naïve.
- Group 4 (EGFRmut, any T790M, any MET, 1L (treatment naïve) 2-3L antineoplastic: EGFRmut NSCLC who failed (defined as intolerance to treatment or documented disease progression) maximum 2 prior lines of systemic antineoplastic therapy
- Group 5 (EGFRmut, T790M-, MET GCN $\geq$ 5, 2L, EGFR TKI resistant): previously documented EGFR activating mutation (e.g., L858R and/or ex19del), T790M negative, MET amplified who have progressed on one prior line of therapy (either to first/second generation EGFR TKIs, osimertinib or other third generation EGFR TKIs) for advanced/metastatic NSCLC disease.

Participants in Phase Ib, Phase II Groups 1, 2 and 3 will take the combination therapy in fasting conditions whilst participants in Phase II Group 4 will take the study treatment with food.

For the purpose of this study, common EGFR activating/sensitizing mutations are L858R point mutation and exon 19 deletions which account for approximately 90% of the cases. Other rare EGFR mutations such as L861Q, G719X, and S768I are also considered activating/sensitizing mutations for enrollment onto the Phase II Group 1, Group 3 and Group 4.

The IRT will also specify medication number of the bottles of capmatinib monotherapy or capmatinib in combination with nazartinib study drug to be dispensed to the participant.

